6 STUDY DESIGN

This is a prospective, open-, single arm, multi-center clinical trial to evaluate the safety and effectiveness of the Cordella PA Sensor System in NYHA Class III Heart Failure Patients.

Subjects will be categorized into three (3) different cohorts, with subjects from Cohort #2 and Cohort #3 below serving as the basis for the primary study analysis:

1. Cohort #1- Previously enrolled **Control Arm** subjects
 - Subjects in this cohort will be unblinded to their PAP measurements and informed about their previous group assignment and continue their Follow-up visit schedule
 - Additionally, subjects will be asked, throughout the remaining Follow-up period, to complete a regular subject survey on their experience with PAP Measurements and PAP Values.
 - Clinicians will be unblinded to their PAP measurements and start managing the patients to target PA pressures per protocol/ CIP and according to GDMT
 - Additionally, the clinical site will be asked to contact the subject on a regular basis to discuss their PAP values
 - Separate subgroup analysis (efficacy and safety) will be performed
2. Cohort #2- Previously enrolled **Treatment Arm** subjects
 - As of **month 12** subjects in this cohort will be able to see their own PAP measurements for the remaining duration of the study.
 - Clinicians will continue to manage their patients to target PA pressures per protocol/ CIP and according to GDMT
 - All primary and secondary safety and effectiveness analyses will be performed
3. Cohort #3- **Newly enrolled** subjects
 - will participate in the Screening/ Enrollment Visit Cordella PA Sensor Implant Visit, and Follow-Up Visits
 - Clinicians will manage the patients to target PA pressures per protocol/CIP and according to GDMT
 - As of **month 12** subjects in this cohort will be able to see their own PAP measurements for the remaining duration of the study.
 - All primary and secondary safety and effectiveness analyses will be performed

All subjects will receive a Cordella PA Sensor Implant and will be followed for 6 month for the Primary Efficacy Endpoint, 6 months for the Safety Endpoints, and will be continued to be followed up to 5 years post implant.

[figure not shown]

Figure 8: Study Design

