6.3 Subject Participation and Study Duration

Subjects will participate in the study for a total of 5 years.

The study started in the Fourth Quarter 2019 (First Implant) and enrollment (Last Implant) is estimated to be completed by First Quarter 2023.

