1.2. Timings of Analyses

Main analysis will be performed after all Cohort #2- Previously enrolled Treatment Arm subjects and Cohort #3- Newly enrolled subjects completed the Month 6(V5) study visit or discontinued earlier. This main analysis will include all endpoints and analyses described in the SAP as far as data allow. The cleaning process will be completed at this stage, saying that the main analysis will be based on clean and coded data. Protocol deviations will be assessed and analysis sets will be defined following Syneos Health SOP (Blind) Data Review and Definition of Analysis Sets (3911) prior to the cut-off date for database (soft) lock. At this stage it will be decided if the analysis based on the Per-protocol population will be performed. Analysis will be performed on all analysis sets deemed relevant for the analysis. Listings will include all data collected until the cut-off date, by visit summaries will include data until V5 (Month 6), summaries (e.g. medication, or adverse events) without visit information will include all data until the cut-off date.

Additionally, an analysis on safety data will be performed once, the first 50 subjects which have been implanted with the Cordella PA Sensor have completed V4, Month 3 and also when 100 subjects have completed V3, Month 1. These safety analyses may occur at the same time depending on the timing of study visits. Analysis will be done on as much as possible clean and coded safety data.

The follow-up (final) analysis is planned after all subjects have completed the final study visit (V9, Year 3) or terminated early from the study.

An independent Data Safety Monitoring Board (DSMB) will review descriptive summaries of accumulating safety and subject disposition data on regular basis. Further description of the DSMB analyses can be found in the DSMB Statistical Analysis Plan Version 3.1 dated 07-Feb-2022 [1] and the DSMB charter Version 4.0 dated 04-Mar-2022 [1]. The study team from Syneos Health Biostatistics will perform the analyses.

The cut-off time point for the safety analysis and first two DSMB meetings expected to be identical. Outputs described in the DSMB SAP will cover the safety and DSMB analysis.

This document is confidential.

2. Study Objectives

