At the Implant Visit (V2), the Cordella PA Sensor, which is pre-mounted on a catheter Delivery System, is delivered according to the system's Instructions for Use. Once deployed, the Sensor PAP readings are calibrated using the system's fluid-filled catheter. The calibration coefficients for that Sensor/subject are stored in a database, allowing for consistent PAP calculations throughout the study duration.

Below enrollment stopping rules will be considered during the study.

- 1) to have sufficient number of women representatives in the study, it is anticipated to include at least 35 % women out of the planned population. Therefore, the inclusion/enrollment of the men subjects will be limited to 65% at the most.
- 2) to have sufficient number of heart failure with preserved ejection fraction (HFpEF) representatives in the study, it is anticipated to include at least 45 % HFpEF subjects out of the planned population.

This document is confidential.

Therefore, the inclusion/enrollment of the heart failure with reduced ejection fraction (HFREF) subjects will be limited to 55% at the most.

Subjects are observed until stable and discharged home with instructions to take their PAP measurements daily (e.g. same time each morning) along with their weight, BP, HR and SpO₂, which are wirelessly transmitted to a secure website. Subjects also receive a Cordella™ PA Sensor System implant card, a Patient User's Manual, and a Technical Support number to contact Endotronix representatives with any questions.

The clinician will contact all subjects on a pre-determined call schedule basis to discuss their health status and all patients will be treated according to GDMT.

Visibility to patients' daily data trends will enable the clinician to proactively manage the patients to target PA pressures per protocol and according to GDMT.

Subjects return for follow up visits at 1, 6, 12, 18, 24 months and Year 3 after the Cordella PA Sensor implant, or until study termination. The 3-month follow-up visit will be performed as remote/ virtual Telemonitoring visit.

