A subject may discontinue his or her participation without giving a reason at any time during the study. Should a subject's participation be discontinued, the primary reason for termination has to be recorded in the Electronic Case Report Form (eCRF). In addition, efforts have to be made to perform all procedures scheduled for the Month 6 (V5) visit if discontinuation is prior to that visit, or the year 3 (V9) visit if discontinuation is after year 2 but before Year 3. Subjects who are withdrawn may be replaced with new subjects for evaluation upon Sponsor approval.

The primary reason for discontinuation or withdrawal of the subject from the study is collected using the following categories:

- Lost to follow-up. The subject did not return to the clinic and attempts to contact the subject were unsuccessful.
- Voluntary withdrawal. The subject wishes to withdraw from the study. The reason for withdrawal, if provided, recorded in the eCRF.
- Principal Investigator withdrawal due to failure to comply with trial requirements or subject is uncooperative or refuses to continue in the trial
- Study termination. The sponsor, Institutional Review Board (IRB), or regulatory agency terminates the study
- Other

After completion of the last study visit (V9) the subject continues to participate in the site-specific Heart Failure Follow-up program.

Main analysis to demonstrate durability of the treatment effect is planned to be performed at the timepoint, when all Cohort #2 and #3 subjects have completed 6 months of follow-up or discontinued study earlier. At this timepoint the complete analysis as defined in the SAP will be performed, including definition of the protocol deviations and analysis sets. The analysis will be done on the clean and coded data.

Once all subjects completed the final study visit (V9) or terminated early from the study, a follow-up analysis will be done. For the follow-up analysis, the complete set of outputs will be refreshed based on the data available at study end.

DSMB meetings are planned for the study and will follow the scheduled defined in the DSMB charter.

This document is confidential.

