8.2. Secondary safety endpoints

- 1) Pressure sensor failure rate throughout the study
- 2) Frequency of serious adverse events throughout the study
- 3) Frequency of implant procedure and procedure related adverse events and serious adverse events

Both secondary endpoints will be evaluated based on the AEs information and covered by AEs outputs.

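### The SAP ties its final analysis to Year 3 although follow-up runs to Year 5, so the study-long safety endpoints would cover Years 4 and 5 only partly and unevenly

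*SAP*

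**What the plan says.** **Protocol.** Section 6.3 states "Subjects will participate in the study for a total of 5 years", and Section 6 says that subjects "will be continued to be followed up to 5 years post implant". Sections 6.5, 8.1 and 8.3.8 and Appendix 14.1 agree, placing V9, V10 and V11 at Years 3, 4 and 5. Section 9 collects adverse events until a subject's participation is complete. The Amendment History dates the extension to Year 5 to version 10.0, 16 December 2022.

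**SAP version 2.1, 17 August 2023.** Section 1.2 says "The follow-up (final) analysis is planned after all subjects have completed the final study visit (V9, Year 3". Section 2.2 repeats the trigger: "Once all subjects completed the final study visit (V9) or terminated early from the study, a follow-up analysis will be done". For that analysis, "the complete set of outputs will be refreshed based on the data available at study end". The same section limits the visit list ("Subjects return for follow up visits at 1, 6, 12, 18, 24 months and Year 3 after the Cordella PA Sensor implant") and treats V9 as the end of study participation: "After completion of the last study visit (V9) the subject continues to participate in the site-specific Heart Failure Follow-up program". Section 5.4 gives visit windows only to Year 3. SAP Appendix 1, however, shows V9 to V11 at Years 3, 4 and 5.

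**Endpoints.** Sections 3.4 and 8.2 list "Pressure sensor failure rate throughout the study" and, over the same period, the frequency of serious adverse events. Section 8.2 says that these are covered by the adverse event outputs.

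**The concern.** The body of the SAP and the protocol disagree on when the study ends, and the SAP's trigger for its last analysis follows the earlier date. No later analysis is specified. Section 10 of the SAP, which lists departures from the protocol, does not mention a stop at Year 3, so nothing presents it as a deliberate choice.

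The cost falls on the long-term safety questions. Protocol 2.1 describes the sensor as a permanent implant, and late sensor failure is something that extended follow-up can show and a 6-month endpoint cannot. If the last pre-specified analysis runs before follow-up is complete, the late data are thin, come mostly from the earliest implants, and have no planned report once they are complete.

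**Working it through.** The SAP states no figure to reproduce here. The check is a comparison of dates, followed by a rough size under stated assumptions.

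**Is it a relic of the amendment log?** No. The SAP is dated eight months after protocol version 10.0, and its Appendix 1 already carries the Year 5 schedule. The schedule table was updated and Sections 1.2, 2.2 and 5.4 were not. The early-discontinuation text in SAP 2.2 also still points to the Year 3 visit, where protocol 7.7.2 points to Year 5.

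**When does each trigger fall?** Protocol 6.3 gives first implant in Q4 2019 and estimates last implant by Q1 2023.
- All subjects through V9: Q1 2023 + 3 years = about Q1 2026.
- All subjects through V11: Q1 2023 + 5 years = about Q1 2028.

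**How much follow-up is missing at the earlier date?** Assumptions:
- 535 implanted (protocol 6.1).
- Five-year survival 50% (protocol 1.1, quoted there from diagnosis of heart failure).
- Constant hazard and no dropout.
- First implant between 2019.75 and 2020.0, and last between 2023.0 and 2023.25, so accrual lasts L = 3.0 to 3.5 years.

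Hazard h = ln 2 / 5 = 0.1386 per year, so S(3) = 0.660 and S(5) = 0.500.

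Planned subject-years per subject: (1 − 0.500)/0.1386 = 3.607. Times 535 = 1,930.

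*Each subject cut at their own V9:* (0.660 − 0.500)/0.1386 = 1.152 lost per subject. Times 535 = 617, and 617/1,930 = 32%.

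*Cut-off when all subjects have reached V9, uniform accrual:* a subject implanted u years before the last one has 3 + u years at the cut-off, and loses (S(3+u) − S(5))/h if u < 2 and nothing otherwise. Integrating u from 0 to 2 gives (1.152 − 2 × 0.500)/0.1386 = 1.099. The total loss is 535 × 1.099 / L:
- L = 3.5: 168 subject-years, 9%.
- L = 3.0: 196 subject-years, 10%.

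*Same cut-off, back-loaded accrual (assumed):* 170 subjects implanted before the single-arm amendment of November 2021 (85 in Cohort #1 and an assumed 85 in Cohort #2) and 365 after it. The later group accrues over 1.14 to 1.39 years and loses on average 0.80 to 0.72 subject-years each, about 290 to 263 in all. The earlier group adds about 8 to 18. Total 271 to 308, or 14–16%.

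**Share of the Year 3–5 window itself, Cohorts #2 and #3, ignoring deaths.** Under uniform accrual the share lost is 1/L, or 29–33%. Under the assumed 85/365 split it is 54–60%.

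**The case against.** The strongest reply is that late data are not excluded. The trigger waits for all subjects to reach V9, by which time the earliest implants are past Year 5. The final outputs use the data then available, and SAP 1.2 says for the main analysis that adverse event summaries take everything up to the cut-off. Neither safety endpoint is capped at Year 3. This stands. A reader might infer that no planned analysis touches Years 4 and 5, or that two of five years are lost for everyone. The documents do not support that: it needs a cut at each subject's own V9, which no SAP text states. The nearest is the sentence in SAP 2.2 on what follows V9, and the protocol keeps collecting data after that visit.

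The inputs are also soft. The survival figure is not measured from implant in NYHA Class III patients, and protocol 6.1 itself expects about 10% dropout by 6 months. The 535 includes Cohort #1, which the SAP's ITT safety set leaves out. Removing it does not change the uniform percentage. It raises the back-loaded one, because the late losses fall on a smaller total: 450 × 3.607 = 1,623 planned, about 267 to 299 lost, 16–18%. So the figures give an order of magnitude only.

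It is also fair to say that V9 is probably stale text, that these endpoints are summarised without hypothesis tests, and that the DSMB reviews safety every six months. But DSMB summaries are monitoring under separate documents and do not replace the endpoint analysis, and a programmer following the SAP would run the final analysis at Year 3.

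**Conclusion.** The contradiction is real and sits in current text. SAP 1.2, 2.2 and 5.4 end at V9/Year 3, against the protocol and SAP Appendix 1 at V11/Year 5. Followed literally, the last planned analysis comes about two years early, and the two study-long safety endpoints are under-covered for Years 4 and 5: early implants contribute, and the last-implanted subjects lose both years.

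The likely size, on the assumptions above, is about 9–10% of planned subject-years under uniform accrual and 14–16% under back-loaded accrual. The 32% figure is an upper bound that applies only under truncation at each subject's own V9. The text mismatch is certain; the size depends on an accrual pattern that the documents do not give.

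The primary endpoints at 6 months and the formally tested secondary endpoint at 12 months are untouched. This should be corrected before the final analysis, but it does not threaten the main result.

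**What to change.** - **SAP 1.2 and 2.2:** name V11/Year 5 as the final study visit, tie the final analysis to it, and state the data cut-off explicitly. If a Year 3 report is wanted, describe it as a separate descriptive analysis that precedes the Year 5 one.
- **SAP 2.2:** extend the visit list to Years 4 and 5, and bring the last-visit and early-discontinuation sentences into line with the protocol.
- **SAP 5.4:** extend the visit windows to Years 4 and 5, as in protocol 8.1 and SAP Appendix 1.

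The cost is SAP wording and, if a Year 3 report is kept, one further run of the outputs. The protocol already collects the data, so no procedure, sample size or tested hypothesis changes. The final analysis moves from about Q1 2026 to about Q1 2028.

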2.1. Study Objective

To demonstrate safety and efficacy of the Cordella PA Sensor System.

2.2. Brief Description

This is a prospective, open-label, single arm, multi-center clinical trial evaluating the safety and efficacy of the Cordella™ Pulmonary Artery Sensor System in New York Heart Association (NYHA) Class III heart failure (HF) subjects compared to a Performance Goal (PG).

All eligible subjects get implanted the Cordella PA Sensor. As part of the Cordella PA Sensor System (CorPASS), it intends to measure, record, and transmit pulmonary artery pressure (PAP) data from NYHA Class III heart failure patients at home to clinicians for assessment and patient-centered HF management, with the goal of reducing heart failure hospitalizations.

The study is planned to be conducted in up to 120 sites in the United States and Europe. The study population includes male and female subjects, ≥ 18 years of age with a diagnosis of NYHA Class III heart failure.

With this amendment to the protocol/CIP, subjects will be categorized into three (3) different cohorts:

1. Cohort #1- Previously enrolled Control Arm subjects
 - Subjects in this cohort will be unblinded to their PAP measurements and informed about their previous group assignment and continue their Follow-up visit schedule
 - Additionally, subjects will be asked, throughout the remaining Follow-up period, to complete a regular subject survey on their experience with PAP Measurements and PAP Values.
 - Clinicians will be unblinded to their PAP measurements and start managing the patients to target PA pressures per protocol/ CIP and according to Guideline Directed Medical Therapy (GDMT)
 - Additionally, the clinical site will be asked to contact the subject on a regular basis to discuss their PAP values
 - Separate analysis (safety and effectiveness) will be performed for Cohort #1
2. Cohort #2- Previously enrolled Treatment Arm subjects
 - As of month 12 subjects in this cohort will be able to see their own PAP measurements for the remaining duration of the study.
 - Clinicians will continue to manage the patients to target PA pressures per protocol/CIP and according to GDMT
 - All primary and secondary safety and effectiveness analyses will be performed
3. Cohort #3- Newly enrolled subjects

This document is confidential.

- Subjects will participate in the Screening/ Enrollment Visit, Cordella PA Sensor Implant Visit, and Follow-Up Visits.
- Clinicians will manage the patients to target PA pressures per protocol/ CIP and according to GDMT.
- As of month 12 subjects in this cohort will be able to see their own PAP measurements for the remaining duration of the study.
- All primary and secondary safety and effectiveness analyses will be performed.

Up to 450 subjects are planned to be enrolled and successfully implanted with the Cordella PA (consisting of subjects from Cohort #2 and Cohort #3 below). These subjects will be the basis for the primary study analysis. Additionally, up to 85 subjects (cross- over from former Control Arm) will continued to be followed in Cohort #1.

To be enrolled into the study, subjects must be receiving stable Guideline Directed Medical Therapy (GDMT) for HF per current American Heart Association (AHA)/American College of Cardiology (ACC) guidelines as standard-of-care for HF therapy in the United States and Europe, with any intolerance documented for at least 30 days. This will be verified by the trial specific PROACTIVE-HF Clinical Eligibility Committee.

Subjects must be diagnosed with heart failure for a minimum of 3 months, are clinically stable, have an increase of NT-proBNP and a HF related hospitalization, HF treatment in a hospital day-care setting, or urgent outpatient clinic HF visit for IV diuretics within 12 month (last hospitalization should be 30 days before Screening /Enrollment)

Potential subjects are to be identified by the Investigator and research staff with the study Inclusion and Exclusion criteria in mind. At Screening, subjects are fully informed on what to expect with study participation to maintain a high study participation retention rate. As part of the study Implant Visit, subjects undergo a training on the at-home use of the Cordella™ Heart Failure System (Cordella System) to ensure compliance with the web-based clinical care management component of the Cordella™ Heart Failure System. Throughout the study, subjects will continue to be followed closely to ensure study compliance as well as continued study participation

At the Screening/ Enrollment Visit, subjects review and sign the informed consent form prior to any study-related procedures performed. Based on Screening Visit results, the Investigator confirms and documents study eligibility for each subject. As part of the study screening process, subjects will be scheduled for a RHC and PA Sensor Implant procedure.

At the Implant Visit (V2), the Cordella PA Sensor, which is pre-mounted on a catheter Delivery System, is delivered according to the system's Instructions for Use. Once deployed, the Sensor PAP readings are calibrated using the system's fluid-filled catheter. The calibration coefficients for that Sensor/subject are stored in a database, allowing for consistent PAP calculations throughout the study duration.

Below enrollment stopping rules will be considered during the study.

- 1) to have sufficient number of women representatives in the study, it is anticipated to include at least 35 % women out of the planned population. Therefore, the inclusion/enrollment of the men subjects will be limited to 65% at the most.
- 2) to have sufficient number of heart failure with preserved ejection fraction (HFpEF) representatives in the study, it is anticipated to include at least 45 % HFpEF subjects out of the planned population.

This document is confidential.

Therefore, the inclusion/enrollment of the heart failure with reduced ejection fraction (HFREF) subjects will be limited to 55% at the most.

Subjects are observed until stable and discharged home with instructions to take their PAP measurements daily (e.g. same time each morning) along with their weight, BP, HR and SpO₂, which are wirelessly transmitted to a secure website. Subjects also receive a Cordella™ PA Sensor System implant card, a Patient User's Manual, and a Technical Support number to contact Endotronix representatives with any questions.

The clinician will contact all subjects on a pre-determined call schedule basis to discuss their health status and all patients will be treated according to GDMT.

Visibility to patients' daily data trends will enable the clinician to proactively manage the patients to target PA pressures per protocol and according to GDMT.

Subjects return for follow up visits at 1, 6, 12, 18, 24 months and Year 3 after the Cordella PA Sensor implant, or until study termination. The 3-month follow-up visit will be performed as remote/ virtual Telemonitoring visit.

A subject may discontinue his or her participation without giving a reason at any time during the study. Should a subject's participation be discontinued, the primary reason for termination has to be recorded in the Electronic Case Report Form (eCRF). In addition, efforts have to be made to perform all procedures scheduled for the Month 6 (V5) visit if discontinuation is prior to that visit, or the year 3 (V9) visit if discontinuation is after year 2 but before Year 3. Subjects who are withdrawn may be replaced with new subjects for evaluation upon Sponsor approval.

The primary reason for discontinuation or withdrawal of the subject from the study is collected using the following categories:

- Lost to follow-up. The subject did not return to the clinic and attempts to contact the subject were unsuccessful.
- Voluntary withdrawal. The subject wishes to withdraw from the study. The reason for withdrawal, if provided, recorded in the eCRF.
- Principal Investigator withdrawal due to failure to comply with trial requirements or subject is uncooperative or refuses to continue in the trial
- Study termination. The sponsor, Institutional Review Board (IRB), or regulatory agency terminates the study
- Other

After completion of the last study visit (V9) the subject continues to participate in the site-specific Heart Failure Follow-up program.

Main analysis to demonstrate durability of the treatment effect is planned to be performed at the timepoint, when all Cohort #2 and #3 subjects have completed 6 months of follow-up or discontinued study earlier. At this timepoint the complete analysis as defined in the SAP will be performed, including definition of the protocol deviations and analysis sets. The analysis will be done on the clean and coded data.

Once all subjects completed the final study visit (V9) or terminated early from the study, a follow-up analysis will be done. For the follow-up analysis, the complete set of outputs will be refreshed based on the data available at study end.

DSMB meetings are planned for the study and will follow the scheduled defined in the DSMB charter.

This document is confidential.

